## **Abstract**

- **Background:** This web-based experimental study aims to investigate the effect of promoting an active (i.e. conscious and autonomous) choice process regarding coping with an increased risk of

cardiovascular disease (CVD) on psychological outcomes, compared to usual care; i.e. a general practitioners' (GP) advice. Coping strategies include: changing one's lifestyle; taking medication; doing both; or changing nothing. An active choice process is expected to increase psychological outcomes compared to a passive choice process (i.e. a simple advice).

- **Methods:** We will recruit adults aged 45-65 years who are not on medication to prevent CVD and who do not have are have had CVD. Participants will be randomized to the intervention – active choice – group or the control – usual care – group. Both groups will be presented a hypothetical CVD risk. In the control group, the risk will be presented as a 31% risk of developing CVD within ten years, whereas the intervention group will be presented an equivalent risk in a different format: a 'heart age' of 16 years older than their actual age. The intervention group will additionally receive information about the meaning of the risk, including its causes and potential consequences, and about the four coping strategies. The pros and cons of each strategy will be presented, followed by a value-clarification exercise. The control group will read a hypothetical advice to change their lifestyle, and to take medication to lower their CVD risk. Participants will receive a questionnaire that assesses psychological outcomes, including 'degree of active choice', commitment, and intention to cope with CVD risk. Intergroup differences will be examined by regression analyses. In addition, we will conduct a process evaluation.
- **Discussion:** If an active choice process regarding coping with an increased CVD risk indeed results in better outcomes compared to an advice, the active choice intervention could be implemented by GP's. GP's could either use it as a tool during their consultation, or send it to their patients, so the patients can read the information and clarify their own values before making a choice. Providing patients with a choice – instead of giving advice – respects their autonomy. Ultimately, it is expected that an active choice process will increase patients' adherence to the chosen option; e.g., a healthier lifestyle or medication use.

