### **Intervention description {11a}**

The intervention group will be presented a hypothetical 'heart age' of 16 years older than their actual age. They are asked to imagine that this heart age really applies to them. Next, participants will receive information about the meaning of the risk, including its causes and potential consequences, and about four coping strategies: changing one's lifestyle; taking medication; doing both; or changing nothing. The pros and cons of each strategy will be presented, followed by a value-clarification exercise.

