## Outcomes {12}

All outcomes will be assessed directly after the intervention. Overview of outcome measures:

Outcome	Number of items	Scale
Intention regarding coping with CVD	1	Nominal; 4 options: Lifestyle change/ Medication use/ Lifestyle change and medication use/ Change nothing
Intention strength	1	Scale of 1 (not strong at all) to 10 (very strong)
Degree of active choice	11	A 5-point scale will be used for the items (1: totally disagree; to 5: totally agree). The average of all 11 items will be used as composite score.
Values congruence	1	A 10-point scale will be used: 1 (not at all) to 10 (totally).
Commitment	3	A 10-point scale will be used: 1 (not at all) to 10 (totally).
Self-efficacy	1	A 10-point scale will be used: 1 (not at all) to 10 (totally).
Response efficacy	2	A 10-point scale will be used: 1 (not at all) to 10 (totally).
Autonomous motivation & controlled motivation	12	The Treatment Motivation Questionnaire will be used. This questionnaire contains 2 subscales: Autonomous motivation and Controlled motivation. Items are on a scale of 1 (not at all true) to 7 (very true).
Knowledge – illness representations	4	4 items on a scale of 1 (totally disagree) to 5 (totally agree).
Risk perception: Cognitive and affective risk appraisal	3	1 item assesses cognitive risk appraisal (on a scale ranging from 'very small risk' to 'very high risk'. 2 items assess affective risk appraisal on a scale of 1 (not at all) to 10 (totally)
Lifestyle intention	1	Nominal; 4 options: Quit smoking; Healthier diet; More physical activity; Other.
Lifestyle intention strength	1	Scale of 1 (not strong at all) to 10 (very strong)
Perceived health	1	Item from RAND-36. Scale: 1 (very bad) to 5 (very good).
Preferred decision-making role	1	Item based the Control Preferences Scale of Degner et al. (1992). Contains 5 options to assess preference for a more passive or more active role in decision-making about treatment.

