### RESEARCH QUESTION

What is the differential impact on psychological outcomes between promoting an active and a passive choice process regarding lifestyle changes and medication use to reduce cardiovascular risk?

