### Statistical analyses

- Before conducting the regression analyses, we will check whether the assumptions have been met:
- Assumptions for linear regression analysis:
  - Dependent variable has a normal distribution
  - Linear relation between independent and dependent variable
  - Also: <https://www.statisticssolutions.com/assumptions-of-linear-regression/>
- Assumptions logistic regression analysis:
  - <https://www.statisticssolutions.com/assumptions-of-logistic-regression/>
- Moreover, we will investigate:
  - Confounding by Age on the 3 primary outcome measures (i.e., degree of active choice, intention strength and commitment). If confounding is found, we will also check whether it applies to the secondary outcome measures, and we will correct for age in the main analyses.
  - Effect modification by gender, educational level (3 levels), health condition (yes/no), and decision making preferences (active/passive) on the 3 primary outcome measures (i.e., degree of active choice, intention strength and commitment). If effect modification is found, we will also check whether it applies to the secondary outcome measures.
- ❖ **Analyses:**
  - **Active Choice**  
Linear regression analysis with condition as independent variable and Degree of Active Choice as dependent variable.
  - **Intention strength**  
Linear regression analyses with condition as independent variable and Intention strength as dependent variable.

- **Commitment**  
Linear regression analysis with condition as independent variable and Degree of commitment as dependent variable.
- **Intention**  
Multinomial logistic regression analysis with condition as independent variable and Intention as dependent variable.
- **Lifestyle Intention: diet**  
Logistic regression analysis with condition as independent variable and intention to change diet as dependent variable.
- **Lifestyle Intention: physical activity**  
Logistic regression analysis with condition as independent variable and intention to change physical activity as dependent variable.
- **Self-efficacy**  
Linear regression analysis with condition as independent variable and Self-efficacy as dependent variable.
- **Response efficacy: lifestyle**  
Linear regression analysis with condition as independent variable and Response efficacy as dependent variable.
- **Response efficacy: medication**  
Linear regression analysis with condition as independent variable and Response efficacy as dependent variable.
- **Autonomous Motivation**  

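### The planned multinomial model for Intention is valid, but none of its coefficients estimates the effect on any lifestyle intention or on any medication intention

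*SAP*

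**What the plan says.** The protocol's outcome table (Outcomes {12}) defines Intention as a single item: "Nominal; 4 options: Lifestyle change/ Medication use/ Lifestyle change and medication use/ Change nothing". The SAP's only analysis of it, under Statistical analyses, is "Multinomial logistic regression analysis with condition as independent variable and Intention as dependent variable". It gives no reference category, no overall test, no percentages per arm and no grouping of categories. Intention is not among the three outcomes that the SAP calls primary (degree of active choice, intention strength, commitment), so it is secondary.

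The SAP's research question compares "promoting an active and a passive choice process regarding lifestyle changes and medication use to reduce cardiovascular risk", so it names both behaviours. The arms hear different things about doing both. In the protocol's Abstract, "The control group will read a hypothetical advice to change their lifestyle, and to take medication to lower their CVD risk". Under Intervention description {11a}, the intervention group is informed "about four coping strategies: changing one's lifestyle; taking medication; doing both; or changing nothing".

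The nearest other analyses are "Logistic regression analysis with condition as independent variable and intention to change diet as dependent variable" and the matching model for physical activity, "Logistic regression analysis with condition as independent variable and intention to change physical activity as dependent variable". These concern components of lifestyle. The SAP has no regression for medication intention.

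**The concern.** The four options form a 2x2 table of lifestyle (yes/no) by medication (yes/no). Everyone who intends medication sits in 'medication use' or in 'both'; everyone who intends lifestyle change sits in 'lifestyle change' or in 'both'. A multinomial coefficient compares one cell with the reference cell. The coefficient labelled 'medication' is therefore about medication only, and the one labelled 'lifestyle' about lifestyle only.

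This matters here because controls are advised to do both, while the intervention arm chooses from four options. Movement between 'both' and a single strategy is a foreseeable effect. Someone who moves from 'both' to 'lifestyle only' has dropped the medication intention and kept the lifestyle intention, and no single coefficient states that. At stake is whether the report can say what active choice does to each of the two intentions named in the research question, and whether the reference category and any grouping are fixed before the data are seen.

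**Working it through.** **Inputs.** Sample size {14} gives 206 men and 156 women per group: 206 + 156 = 362 per arm, and 2 x 362 = 724, which agrees with the stated total. That calculation concerns degree of active choice; only n = 362 is used here. The documents give no expected shares for Intention, so every share below is an assumption, in the order lifestyle only / medication only / both / nothing.

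**Formulas.** With condition as the only predictor, the multinomial odds ratio for category j against reference r is (intervention share j / intervention share r) / (control share j / control share r). The SE of its log is the square root of the sum of the reciprocals of the four cell counts. The risk difference has SE = sqrt[p1(1-p1)/362 + p0(1-p0)/362].

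**Main illustration: control 35/5/55/5%, intervention 50/5/39/6%.**

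- Any medication: control 5 + 55 = 60%, intervention 5 + 39 = 44%. Difference -16 points; SE = sqrt(0.60 x 0.40/362 + 0.44 x 0.56/362) = 0.0367; 95% CI -23.2 to -8.8 points.
- Any lifestyle: 35 + 55 = 90% against 50 + 39 = 89%. Difference -1 point, 95% CI -5.5 to +3.5.
- Planned model, reference 'Change nothing':
  - lifestyle only: (0.50/0.06)/(0.35/0.05) = 1.19 (0.61 to 2.31)
  - medication only: (0.05/0.06)/(0.05/0.05) = 0.83 (0.34 to 2.05)
  - both: (0.39/0.06)/(0.55/0.05) = 0.59 (0.31 to 1.14), z = -1.56
- Planned model, reference 'both': lifestyle only (0.50/0.39)/(0.35/0.55) = 2.01 (1.47 to 2.76), z = 4.38.
- Overall likelihood-ratio test: the four categories contribute 9.63 + 0.00 + 9.91 + 0.33 = 19.87 on 3 df, p about 0.0002.

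On the same data, no coefficient is significant with one reference and one is strongly so with another. The overall test sees a difference without saying that it lies in medication.

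**Direction can differ: control 30/5/55/10%, intervention 45/8/37/10%.** Any medication falls from 5 + 55 = 60% to 8 + 37 = 45%, odds ratio (0.45/0.55)/(0.60/0.40) = 0.55 (0.41 to 0.73). The medication-only odds ratio is (0.08/0.10)/(0.05/0.10) = 1.60 (0.76 to 3.38) against 'Change nothing' and (0.08/0.37)/(0.05/0.55) = 2.38 (1.27 to 4.45) against 'both'. Both lie above 1.

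**A mild case: control 40/10/30/20%, intervention 45/6/35/14%.** Any lifestyle rises from 70% to 80%, odds ratio 1.71, power 0.88. Against 'Change nothing', the two lifestyle-containing coefficients are 1.61 and 1.67, with power 0.59 and 0.62. They point the right way and lose only power.

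**The case against.** A reader might infer that the multinomial model is wrong for this outcome. It is not: it is the standard model for one nominal item with exclusive options, and 'lifestyle only' against 'both' is a real contrast, because the intervention offers them as separate choices. With condition as sole predictor the model is saturated, so it reproduces the four shares per arm, and the two combined percentages follow by addition. All of this stands.

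A reader might also infer that the planned analysis would fail to see a large fall in medication intention. The documents do not support that. The overall test detects the main illustration, and so do the coefficients when 'both' or 'lifestyle' is the reference. With a larger assumed shift (control 10/5/80/5%, intervention 50/5/38/7%), the coefficient for 'both' against 'Change nothing' is itself significant: (0.38/0.07)/(0.80/0.05) = 0.34 (0.18 to 0.64).

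Nor do the documents show that the trial would wrongly report a rise in lifestyle intention. The odds ratio of 2.01 correctly says that more people prefer lifestyle alone to both. It misleads only if read as any lifestyle intention, and the SAP plans no such statement.

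Finally, the SAP's hypothesis asks only for a different impact, which an overall test would serve. But the SAP does not specify that test, and a significant result would not say which behaviour changed or in which direction. That part of the concern survives.

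**Conclusion.** The point holds as a cheap improvement to the analysis of a secondary outcome. The primary analyses are untouched. No coefficient in the plan estimates the effect on any lifestyle or any medication intention, and with the reference category unstated, the single odds ratios can be imprecise or point away from the change in the behaviour they appear to name.

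That this can happen follows from the item's structure. How much it matters rests on assumed shares at 362 per arm: in the illustrations it ranges from a 16-point fall in any medication intention with no significant coefficient against 'Change nothing', to a modest loss of power with the direction correct. The documents give no basis for choosing between these cases.

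**What to change.** In the SAP, under Intention:

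1. Keep the multinomial regression. Name its reference category, and report the overall 3-df test and the four percentages per arm.
2. Add two prespecified binary contrasts on all participants: any lifestyle change ('lifestyle' or 'both' against the rest) and any medication use ('medication' or 'both' against the rest). Fit each by logistic regression on condition, and report the risk difference with its 95% CI.

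The multinomial odds ratios stay in the report, read as contrasts between exclusive options. The cost is a few lines of SAP text and two short regressions on an item already collected. The downside is two more tests among the secondary outcomes.
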